3. EXPERIMENTAL DESIGN

Participants will be randomised into a cross-over design with two study days corresponding to two conditions: larger portion size condition or smaller portion size condition. Each study day will last one day and be separated by a minimum 1-week and maximum 6-week washout period. The two study days will be scheduled for the same day each week. On both days, participants will be served all meals *ad libitum* in the lab (including breakfast and second helpings) and will be provided with snacks to consume outside of the lab – but only the size of the initial portion of the main meal provided for lunch and dinner will be manipulated. Energy intake from all meals and snacks will be recorded.

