5. METHODS

5.1. Test meals

The portion-manipulated test meals will consist of a pasta-based dish for lunch (3 cheese pasta), and a dish served with rice for dinner (chilli con carne), see Table 1 for more information about the dishes. The portion sizes are informed by pilot studies, including pilot studies conducted to assess the norm range, with portions in the larger portion size condition from the mid-higher end of the range, and portion sizes in the smaller portion size condition from the lower end of the norm range (see **Appendix A**).

Table 1. Portion sizes for each portion-manipulated dish in g and kcal

	Larger portion size (100%)			Smaller portion size (67%)		
	g	kcal	£	g	kcal	£
Lunch						
3 cheese pasta	563	816	2.46	375	544	1.64
Dinner						
Chili con carne & rice	437	509	0.90	291	339	0.60
Dinner including cheese and vegetables on the side (totals)	557	737	1.24	411	568	0.94

On each study day, all participants will receive the same *ad libitum* breakfast in the lab (initial serving providing 1437 kcal) and the same snack box for consumption away from the lab throughout the day (providing 906 kcal). At lunch, participants will have the opportunity to serve themselves more of the main dish. At dinner, participants will be served their main dish with a side of vegetables and they will also have the opportunity to request seconds of the main dish. After their dinner a dessert buffet with three options will be provided (providing 1528 kcal). Chilled water (500mL) will be served with each in-lab meal. The complete study menu can be found in SEP_portion_size MENU_UPDATED_TL.xlsx.

Participants will be requested 1/ not to consume any additional food apart from the items provided as part of the study, and 2/ drink only tea, coffee, and no calorie drinks (water) as they usually would.

Note for each self-service breakfast meal we will also vary the size of the dishware (smaller vs larger), the results of which will be reported in detail elsewhere. Given evidence to date (e.g. [47,48]), we expect this to have no impact on energy intake at breakfast, and this will be tested in analyses (see analysis plan). Manipulation of dishware size (smaller followed by larger dishware size

vs larger followed by smaller dishware size) will be fully counterbalanced with the order of portion size presentation (smaller followed by larger portions vs larger followed by smaller portions).

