RANDOMISATION	
 ▪ Participants will be randomly assigned to receive the larger portion sizes at the first experimental session and the smaller portion sizes at the second experimental session or vice versa. ▪ A randomisation sequence will be created using Random Allocation Software [35] with a 1:1 allocation stratified by highest educational qualification (Group 1: low ≤ A level, 18-25 years; Group 2: low ≤ A level, 26+ years, Group 3: ≥ degree, 18-25 years, Group 4: ≥ degree, 26+ years). ▪ The allocations will be placed inside envelopes for each group; the envelopes will be sequentially opened each time a participant from one group consent to take part in the study. ▪ Participants' two experimental sessions should take place on the same day of the week
STUDY DAY 1	
 ▪ Remind allowed food / drink, physical activity restriction and install the FitBit ▪ Sleep, mood, and hunger ratings ▪ Breakfast 30 minute session between 7 am and 10:30 am ▪ Snack box 
 ○ Provide the snack box after breakfast ▪ Lunch 30 minute session (between 12pm and 2pm) ▪ Dinner 30 minute session (between 5pm and 7pm – at least 4 hours after lunch) ▪ Organise the following steps: 
 ○ Remind the date of the next session (washout)
WASHOUT SESSION	
 ▪ Participants return FitBit device and snack box ▪ Check if any additional foods/drinks consumed ▪ Remind participants about date of next session (Study Day 2)

STUDY DAY 2	
 ▪ Remind allowed food / drink, physical activity restriction and install the FitBit ▪ Sleep, mood, and hunger ratings ▪ Breakfast 30 minute session between 7 am and 10:30 am ▪ Snack box 
 ○ Provide the snack box after breakfast ▪ Lunch 30 minute session (between 12pm and 2pm) ▪ Dinner 30 minute session (between 5pm and 7pm – at least 4 hours after lunch) ▪ Organise the following steps: 
 ○ Remind the date of the next session (final session)

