7. STATISTICAL ANALYSIS

All statistical analyses will be performed using SPSS (Version 26.0). The level of significance will be set at $p < 0.05$ for primary analyses and $p < 0.01$ for secondary analyses to account for multiple testing.

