7.3. Missing data

We do not anticipate missing data on energy intake due to participant non-attendance (if a participant misses a meal and it is not possible to reschedule for a later time that day, they will be required to begin that study day again). Every effort will be made to keep the number of missing data due to researchers' error to the lowest. The extent of the missing data will be reported. We plan to analyse complete cases only.

Missing data on other variables will not be allowed by the experimental procedure because the record for each participant will be checked after each study day and the participants will be asked to provide their answers again if case of any missing data.

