7.4.2. Sensitivity analyses

Sensitivity analyses will be conducted to examine whether the pattern of results from the main analyses differ after 1/ excluding participants guessing the aims of the study, 2/ excluding outliers on main outcome variables (identified as those with a value $>$ 3SD from condition mean) and influential cases (identified as those with a Cook's distance $>$ 1, indicating a multivariate outlier [37], 3/

substituting SEP measure (highest educational qualification, \leq A level, $>$ A level) with alternative measures of SEP (level of education – composite score, subjective socioeconomic status (1-10), and household income).

The main analyses will also be repeated controlling for any non-SEP based demographic variables (e.g. BMI, age) that significantly differ between the higher vs. lower SEP groups in order to examine if results remain consistent. To examine whether the order that portions are presented impacts the findings, the main analyses will be repeated with an additional 2-level between-subjects factor (portion size order: smaller, larger vs larger, smaller). Finally, the main analyses will be repeated with dishware size as an additional 2-level within-subjects factor (dishware size: smaller vs larger).

We will report whether sensitivity analyses result in deviations from the pattern of significance to the main analyses (i.e., any significant differences between conditions becoming not significant, and vice versa).

Note if $>30\%$ participants guess the study aim we will include aim guessing as a between-subjects factor in ANOVA rather than use listwise removal.

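### The dishware sensitivity ANOVA in section 7.4.2 cannot be fitted as written, because each participant supplies only two of the four portion-by-dishware cells

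*Combined protocol and SAP*

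**What the plan says.** Section 3 sets up a crossover with "two study days corresponding to two conditions: larger portion size condition or smaller portion size condition". Section 5.1 adds a second manipulation: breakfast dishware is smaller on one study day and larger on the other. The order of dishware sizes "will be fully counterbalanced with the order of portion size presentation". On the expected result, section 5.1 states that "we expect this to have no impact on energy intake at breakfast, and this will be tested in analyses (see analysis plan", and it reserves the detailed dishware results for another report.

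The main analysis (section 7.4.1) is a mixed ANOVA on daily energy intake, with portion size within subjects and SEP between subjects. Daily intake includes breakfast (section 7.2.1). Section 7.4.2 then says that "the main analyses will be repeated with dishware size as an additional 2-level within-subjects factor (dishware size: smaller vs larger". Dishware appears nowhere else in section 7. On software, section 7 states "All statistical analyses will be performed using SPSS (Version 26.0"; on missing data, section 7.3 states "We plan to analyse complete cases only". No mixed-effects model is named.

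Table 2 in section 6 describes randomisation to portion order: "A randomisation sequence will be created using Random Allocation Software [35] with a 1:1 allocation stratified by highest educational qualification". It does not mention dishware order.

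**The concern.** A repeated-measures ANOVA that crosses two 2-level within-subjects factors needs four measurements per person. This design yields two, because portion size and dishware size change together from one day to the other. The specified model has no participant with the data it needs.

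What is at stake is the dishware check. Breakfast counts towards the primary outcome, so dishware is a second manipulation acting on that outcome, and 7.4.2 holds the only analysis of it. If the analysis fails when it is attempted, someone has to choose a substitute model and outcome at that point, possibly with the data in view. Section 7.4.2 also commits to reporting whether each sensitivity analysis changes the pattern of significance. This one would have nothing to report.

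**Working it through.** **1. Which cells each participant fills.** Section 5.1 crosses two portion orders with two dishware orders, giving four sequences.

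| Portion order | Dishware order | Day 1 (portion, dish) | Day 2 (portion, dish) | Pairing |
|---|---|---|---|---|
| smaller, larger | smaller, larger | smaller, smaller | larger, larger | matched |
| smaller, larger | larger, smaller | smaller, larger | larger, smaller | mismatched |
| larger, smaller | smaller, larger | larger, smaller | smaller, larger | mismatched |
| larger, smaller | larger, smaller | larger, larger | smaller, smaller | matched |

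Every sequence fills exactly two of the four cells. With balanced pairings each cell holds 23 of 46 participants, or 30 of 60. Participants with all four cells: 0 of 46 and 0 of 60, whatever the balance, dropout or effect size.

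**2. What the data can estimate.** I checked the rank of the design matrix with one column per participant and two observations each.

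| Model (with participant effects) | N=46 | N=60 |
|---|---|---|
| portion, portion × SEP, dishware, dishware × SEP | rank 50 of 50 columns; residual df 92 − 50 = 42 | rank 64 of 64; residual df 120 − 64 = 56 |
| plus portion × dishware and portion × dishware × SEP | rank 50 of 52 | rank 64 of 66 |

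The additive dishware terms are estimable. The two portion × dishware terms are constant within a person and so aliased with participant. A repeated-measures ANOVA routine given both within factors on simulated data of this design stopped with a collinearity error.

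**3. Recoding.** Let d be a participant's intake on the larger-portion day minus intake on the smaller-portion day, P the portion effect and D the dishware effect. In the matched pairing d has mean P + D; in the mismatched pairing, P − D. Hence D is half the difference between the two pairing means of d, which is what a portion × pairing term tests. On simulated data with N=46, this and the additive model gave the same dishware coefficient (−0.0829 in both).

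**4. The plan's sample size and the cost of recoding.** Inputs from section 7.6: f = 0.175, two-day correlation r = 0.7, α = 0.05, 85% power. The noncentrality is λ = f² × N × 2/(1 − r).

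- N=46: 0.030625 × 92/0.3 = 9.39
- N=60: 0.030625 × 120/0.3 = 12.25

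| | Error df, main model (N − 2) | Power | Error df, with pairing (N − 4) | Power |
|---|---|---|---|---|
| N=46 | 44 | 85.02% | 42 | 84.94% |
| N=60 | 58 | 93.08% | 56 | 93.05% |

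The plan's minimum of 46 is reproduced.

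**5. Precision of the repaired check.** With balanced pairings the standard error of D is s/√N, where s is the residual SD of d. The 95% half-width is t(0.975, N − 4)/√N in units of s: 0.2975 at N=46 and 0.2586 at N=60. For scale, the planned portion effect in the same units is 2f/√(2(1 − r)) = 0.35/√0.6 = 0.4518. The half-width is therefore 0.2975/0.4518 = 66% of that effect at N=46, and 0.2586/0.4518 = 57% at N=60.

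**6. What counterbalancing leaves behind.** With n1 matched and n2 mismatched participants, the mean of d is P + D(n1 − n2)/N. The share of D left in the portion contrast is 0 at 23/23 and 2/46 = 4.3% at 24/22. For portion × SEP, what matters is the difference between the two SEP groups' imbalances. With 23 per group, an equal split within a group is impossible. At 12/11 in one group and 11/12 in the other, the overall split is 23/23, but the share left in portion × SEP is 1/23 + 1/23 = 8.7% of D (taking D as the same in both groups).

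**The case against.** The strongest reply is that dishware does vary within subjects, that 7.4.2 names neither a data layout nor a portion × dishware interaction, and that an additive dishware term is estimable. All of that is true. But the instruction is to repeat a mixed ANOVA with a further within-subjects factor. Reaching the additive term requires a recoded factor or a mixed-effects model, and the plan specifies neither.

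Second, the complete-case rule in section 7.3 concerns intake that should have been recorded and was not, rather than cells the design never creates. That is a fair reading, and the point does not need the rule: step 1 gives zero usable participants from the design alone.

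Third, section 5.1 promises a test on breakfast intake. With dishware as the only within factor, that test would run. It would, but section 7 does not contain it. The mismatch between breakfast and daily intake is a further reason to rewrite the sentence.

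Fourth, the consequences are small: this is one of several sensitivity analyses, on a counterbalanced factor expected to do nothing, with details to be reported elsewhere. The workable substitutes also agree with each other, so there is little room for a favourable choice of model. This stands and limits the weight of the point. It does not give the plan an analysis that runs.

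**Conclusion.** The point holds. The dishware analysis in 7.4.2 cannot be fitted as specified: 0 of 46 and 0 of 60 participants have the four values it needs. This rests only on two study days per person and one dishware size per day, both stated in the plan.

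The damage is confined to the check. The primary portion × SEP model and the sample size stand, and counterbalancing remains the main protection. That protection is not always exact for portion × SEP: up to 8.7% of any dishware effect could remain under the illustrative 12/11 and 11/12 split. A check that runs is therefore worth having. Even repaired, it will be coarse, with a half-width of about 0.30 SD of the within-person difference at N=46 (0.26 at N=60). It should be reported as an estimate with its interval, since a non-significant result would not show that dishware has no effect. The sentence should be corrected before analysis.

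**What to change.** In 7.4.2, replace the within-subjects dishware factor with a two-level between-subjects factor, portion-dishware pairing: larger dishware on the larger-portion day, or larger dishware on the smaller-portion day. Fit a portion × SEP × pairing mixed ANOVA and state how its terms are read:

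- portion × pairing estimates the dishware effect;
- portion × pairing × SEP estimates dishware × SEP;
- the pairing main effect carries portion × dishware, tested against between-subject error.

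Section 7.4.2 already handles portion order with a between-subjects factor, so the approach is in keeping with the plan. For the dishware terms, an equivalent choice is a linear mixed model with portion, SEP, portion × SEP, dishware, dishware × SEP and a participant random intercept.

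Name the outcome as breakfast intake, daily intake or both; the same model serves each. As an optional clarification, Table 2 could state that allocation is to the four portion-order by dishware-order sequences, to match section 5.1. Four equal sequences are possible at 60 (15 each) but not at 46, which is not divisible by four.

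The cost is one sentence in 7.4.2, one optional sentence in Table 2, and two error degrees of freedom in the sensitivity model. The primary model, the sample size and the data collected do not change.

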7.6. Sample size

In a previous study that used the same basic methodology but investigated the PSE over a 5-day period [39], the main effect of portion size on daily energy intake was partial $\eta^2 = 0.41$ – considered a statistically large effect size. From other studies examining shorter time frames, the effect of portion size on energy intake is medium-sized [7, 57]. To be conservative we will power the present study to be able to detect a small to medium size main effect of portion size on daily energy intake ($f=0.175$, $p < .05$, 85% power, within-subject correlation of 0.7 conservatively estimated from [39]), resulting in a minimum sample size of 46 participants. As there is limited evidence on the size of moderating effect of SEP on portion size, this sample size also provides adequate power to detect the same small to medium sized portion size and SEP interaction (within-between-subject interaction) on energy intake. Due to on-going COVID restrictions there is uncertainty over recruitment rates and it may be plausible to recruit more participants into the study. If it is feasible in the time frame of the project, we will aim to recruit up to a further 14 participants, resulting in a final $N=60$. This decision will be made prior to conducting any data analyses. Increasing sample size by approximately 30% would address uncertainty for power analysis parameters (e.g. a smaller than

anticipated sized effect being observed in the study) by increasing power. Furthermore, empirical estimates of sample sizes needed for reasonable power (e.g. 80%) in mediation analyses indicate that a sample of ≈ 60 would be sufficient to detect mediation through pathways that are medium and above in statistical size using bias-corrected bootstrap tests [40].

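### Section 7.4.2 judges sensitivity analyses only by change of significance, which mixes lost power with lack of robustness when aim guessers are removed and misses shifts in the estimate

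*Combined protocol and SAP*

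**What the plan says.** Section 7.4.2 lists the sensitivity analyses. Two remove participants: one drops those who guess the aim, the other drops outliers (more than 3 SD from the condition mean) and influential cases (Cook's distance above 1). The rest remove nobody by definition: alternative SEP measures, adjustment for demographic variables, portion order and dishware size.

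The comparison with the main analysis is described once, as reporting "deviations from the pattern of significance to the main analyses", explained as "any significant differences between conditions becoming not significant, and vice versa". No effect estimate, confidence interval or margin is named.

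Removal of aim guessers is capped: "if $>30\%$ participants guess the study aim we will include aim guessing as a between-subjects factor" instead of removing them.

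Section 7 sets the threshold: "The level of significance will be set at $p < 0.05$ for primary analyses". Section 7.6 plans for f = 0.175, 85% power and a within-subject correlation of 0.7, "resulting in a minimum sample size of 46 participants", and adds that "this sample size also provides adequate power to detect the same small to medium sized portion size and SEP interaction". Recruitment may go further: "we will aim to recruit up to a further 14 participants, resulting in a final $N=60".

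**The concern.** A sensitivity analysis should show whether the answer changes when a doubtful feature of the data is taken away. The answer here is the portion size effect (PSE, larger minus smaller condition) and its difference between SEP groups. The stated criterion looks only at which side of 0.05 the p-value falls.

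This can fail in two directions. When aim guessers are removed, the standard error grows, so p can cross 0.05 although the estimate has not moved for any real reason. In the other direction, an estimate can shrink materially and stay significant, and the criterion records no deviation. The second failure applies to every listed analysis, including those that keep all participants.

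At stake is the statement about robustness, above all for the portion size by SEP interaction, which is the study's new question. The primary test itself is not at stake.

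**Working it through.** **Inputs.** From section 7.6: f = 0.175, ρ = 0.7, N = 46 or 60. From section 3: m = 2 conditions. From section 7: α = 0.05. From section 4.1: SEP groups split 50:50. From section 7.4.2: removal up to 30%. *Assumed:* the number removed, because the documents give no expected share of aim guessers.

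**Step 1: reproduce the plan's figure.** For the within-subject F test with two groups, λ = f²·N·m/(1−ρ) on (1, N−2) degrees of freedom.

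- N = 46: λ = 0.030625 × 46 × 2 / 0.3 = 9.39, power 0.850.
- N = 45: λ = 9.19, power 0.842.

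The minimum of 46 is confirmed. The interaction at the same f has the same λ and degrees of freedom, hence the same power. The implied standardised paired difference is dz = √(λ/N) = √(9.39/46) = 0.452.

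**Step 2: power after removal, same true effect.**

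- 46 to 33 (13 removed): λ = 6.74, power 0.71.
- 46 to 32 (14 removed): λ = 6.53, power 0.70.
- 60 to 42 (18 removed): λ = 8.575, power 0.82.

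On the cap: 13/46 = 28.3% and 14/46 = 30.4%, so 13 is the largest removal strictly inside 30% at N = 46. At N = 60, 18/60 = 30.0% is allowed.

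**Step 3: how often significance status changes when nothing has changed.** Trials were simulated (at least 20,000 per setting) with normal change scores and the same true effect whether or not a participant is removed. Participants were removed at random, and the same tests were run before and after at p < 0.05. Both the PSE and the interaction were set at f = 0.175.

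| N | Removed | One test changes status | Either test changes status |
|---|---|---|---|
| 46 | 2 | 4–5% | 9% |
| 46 | 5 | 8% | 15% |
| 46 | 9 | 13% | 24% |
| 46 | 13 | 18% | 33% |
| 46 | 14 | 19% | 35% |
| 60 | 3 | 3% | 6% |
| 60 | 6 | 5% | 9% |
| 60 | 12 | 9% | 16% |
| 60 | 18 | 13–14% | 25% |

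Most changes are losses. With 14 of 46 removed, 17.5% of trials lose significance and 1.6% gain it.

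**Step 4: other effect sizes.**

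- *Interaction at half the design size (f = 0.0875), N = 46.* Of the significant interactions, 21% are lost with 5 removed and 41% with 14 removed, against 8% and 21% at the design size. The overall rate of status change is 10% and 18%, because fewer trials are significant to begin with.
- *Main effect as large as the cited partial η² of 0.41.* f = √(0.41/0.59) = 0.83. Even if 0.83 is read as dz, power with 33 participants is about 0.996, so status changes in under 1% of trials.

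**Step 5: the outlier rule.** Under normality, 0.0027 of values lie beyond 3 SD. With two values per participant, the expected number removed is 46 × 2 × 0.0027 = 0.25, or 60 × 2 × 0.0027 = 0.32. Random removal of many participants does not describe this analysis.

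**Step 6: shifts that are missed.** At N = 46 with nobody removed, the smallest significant standardised effect is 2.015/√46 = 0.297. A primary estimate at the design value of 0.452 could fall to just above this, a drop of 1 − 0.297/0.452 = 34% with the SD unchanged, and no deviation would be recorded.

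**The case against.** **The sentence is a disclosure rule.** It promises to report changes of significance. It does not overturn the primary result or label it non-robust, and it does not forbid estimates. This stands: a reader might infer that a lost p-value would cancel the finding, but the text does not say so. What remains is that the plan commits to no other comparison.

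**The design limits the problem.** The cover story, the filler tasks and portions chosen to look normal are meant to keep aim guessing low, and the 30% switch bounds removal. This also stands. A reader might infer that removal with no real change will often be reported as a deviation. The documents do not support that, because they give no expected share of aim guessers. With 2 to 5 of 46 removed the rate is 4–8% per test.

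**Removing outliers need not cost power.** This is correct. The 3 SD rule should remove very few people, and removing genuine outliers can reduce variance and raise power. The lost-power argument therefore belongs to the aim-guesser analysis.

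**The main effect may be large.** Section 7.6 calls f = 0.175 conservative, and at the cited 0.41 the main effect is practically immune. The interaction has no such protection: section 7.6 concedes that evidence on its size is limited.

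**Conclusion.** The point holds as a minor one. As written, the comparison in section 7.4.2 cannot separate lost power from lack of robustness when aim guessers are removed. In all the sensitivity analyses, it can miss a material shift that stays on one side of 0.05.

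At the design effect, the chance that one test changes status with nothing real changed is about 4–19% at N = 46 (2 to 14 removed; 18% at 13, the most inside the cap) and about 5–13% at N = 60 (6 to 18 removed). A significant interaction is lost more easily if its true size is below the assumed one; the rate is near zero for a main effect as large as the cited one. These figures assume random removal, normal change scores, an equal true effect in those removed and those kept, and an assumed removal share.

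The primary analysis, its sample size and its test are not affected.

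**What to change.** Replace the sentence on the pattern of significance in section 7.4.2 with:

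> For each sensitivity analysis we will report the PSE and the SEP difference in PSE (kcal) with 95% CIs beside the primary estimates, and robustness will be judged by the direction and size of the shift in the estimate, not by a change in significance alone. For alternative SEP measures on a different scale, we will compare direction and a standardised estimate.

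The last sentence is needed because subjective status (1–10), the education composite and income do not give a kcal difference comparable with the binary contrast.

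A margin that calls an estimate deviant only if it falls outside the primary 95% CI should not be used. At N = 46 and the design effect, the half-width is 0.297/0.452 = 66% of the effect. In 40,000 simulated trials with random removal, it flagged none with up to 7 removed and under 0.1% with 13. It would be nearly blind to the shifts of interest.

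A better yardstick for aim-guesser removal is the chance SD of the shift, SE × √(q/(1−q)), where q is the share removed and SE = 1/√46 = 0.147 in standardised units. With 5 removed, 0.147 × √(5/41) = 0.051, or 11% of 0.452. With 14 removed, 0.147 × √(14/32) = 0.098, or 22%.

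Cost: SAP wording and one results table, with no new data. The downside is a less mechanical judgement.

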7.2.3. Other variables

BMI. Calculated as weight (kg) / Height (m²)

Aim guessing. Participants who identify the aim of the study as being to examine the influence of portion/meal size on food intake/appetite will be coded as being aware of the study aims. Responses will be independently coded by two researchers, with discrepancies in coding decisions resolved by a third researcher.

Manipulation awareness. Two binary variables: self-reported awareness (0: unaware, 1: aware) and observed awareness (0: wrong answer to ordering task, 1: right answer to the ordering task).

Liking, familiarity, and normality ratings. Scores range: 1 to 7.

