7.4. Primary analyses

7.4.1. Confirmatory analyses

To be consistent with previous studies we ran investigating the effect of SEP on intended energy consumption (e.g [45]), the primary measure of SEP used in our primary analysis will be highest educational qualification (binary – lower vs higher).

A mixed ANOVA will be used to test the effect of portion size (categorical: larger, smaller; within-subject), SEP (categorical: lower (\leq A level), higher ($>$ A level), between-subjects), the interaction portion size*SEP on daily energy intake. If the interaction between portion size*SEP is significant the analysis will be stratified by SEP (\leq A level, $>$ A level) and two repeated-measures t-tests will be used to examine the effect of portion size (larger vs smaller) on daily energy intake in the two groups of participants separately. We will not correct for multiple comparisons as we specified a priori hypotheses.

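### Above 30% aim guessers, the awareness check in 7.4.2 no longer estimates the portion effect in unaware participants

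*Combined protocol and SAP*

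**What the plan says.** The primary model is in 7.4.1: "A mixed ANOVA will be used to test the effect of portion size (categorical: larger, smaller; within-subject), SEP" and their interaction, on daily energy intake. Section 7.2.3 makes aim guessing a two-level variable: participants who identify the purpose "will be coded as being aware of the study aims".

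Section 7.4.2 then has two rules for them. The first sensitivity analysis is "excluding participants guessing the aims of the study". The closing note of the same section changes this once more than 30% guess: "we will include aim guessing as a between-subjects factor in ANOVA rather than use listwise removal".

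The outcome of each check is judged by significance: "We will report whether sensitivity analyses result in deviations from the pattern of significance to the main analyses". The rule covers changes in both directions.

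The plan names SPSS 26 but no sum-of-squares type. It does not say whether aim guessing is crossed with SEP, whether the portion by aim-guessing term will be interpreted, or why the switch is at 30%.

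**The concern.** The two rules answer different questions. Removal estimates the effect in people who did not know the purpose. Adding a factor keeps the guessers, and the portion main effect from that model is an average over both groups. The study uses a cover story, so awareness is a threat that the plan itself recognises. Once guessing is common, the result set against the main analysis no longer shows whether the effect exists without awareness. An effect produced by guessers alone could then be reported as unchanged by the check.

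**Working it through.** **Inputs.** From 7.6: N = 46 (possibly 60), f = 0.175, within-subject correlation 0.7, 85% power. From 4.1: half the sample in each SEP group. From 7: significance at 0.05 for primary analyses, taken here to apply to their repeats in 7.4.2. Assumed: Type III tests, the share of guessers, and their effect; the documents give none of these.

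**The plan's own figure.** λ = f²·N·2/(1 − ρ) = 0.030625 × 92/0.3 = 9.39 on (1, 44) df gives power 0.850, so 46 is reproduced. The planned effect in SDs of the day difference (larger minus smaller) is 2 × 0.175/√(2 × 0.3) = 0.45.

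**Weight of guessers in the portion main effect.** Let p be their share, and D_g and D_u the mean day differences in guessers and unaware participants.
- Primary: p·D_g + (1 − p)·D_u.
- Removal: D_u.
- Aim factor, Type III: ½·D_g + ½·D_u, with or without SEP*aim.

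| Guessers | Primary | Factor | Ratio |
|---|---|---|---|
| 14/46 | 0.304 | 0.50 | 1.64 |
| 19/60 | 0.317 | 0.50 | 1.58 |
| 24/60 | 0.40 | 0.50 | 1.25 |
| 30/60 | 0.50 | 0.50 | 1.00 |
| 36/60 | 0.60 | 0.50 | 0.83 |

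At N = 46, 13 guessers (28%) are removed and have weight 0; 14 (30.4%) have weight 0.50.

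**Weight in portion size*SEP.** It is 0.50 only if SEP*aim is in the model. Without that term it is 0.304 at 14/46 with guessers split evenly by SEP, and 0.292 at 19/60 split 6 and 13.

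**Consequence if only guessers respond.** Take D_u = 0, a guesser effect of 0.8 SD, SD of the day difference 1 within each aim group, and 15 of 46 guessing.
- Primary: mean 0.8 × 15/46 = 0.261. The mixture variance is 1 + 0.64 × 0.326 × 0.674 = 1.14, so SE = √(1.14/46) = 0.157 and mean/SE = 1.66. Against a critical value near 2.02, power is about 0.36.
- Factor: mean 0.40, SE = ½√(1/15 + 1/31) = 0.157, ratio 2.54, power about 0.70.
- Portion by aim term: 0.8/√(1/15 + 1/31) = 2.54, power again about 0.70.
- Unaware only: 0.05.

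Simulation (at least 20,000 runs per setting) gives these chances of a significant portion effect:

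| Guessers | Primary | Removal | Factor |
|---|---|---|---|
| 14/46 | 0.32 | 0.05 | 0.68 |
| 15/46 | 0.36 | 0.05 | 0.70 |
| 19/60 | 0.44 | 0.05 | 0.81 |
| 24/60 | 0.63 | 0.05 | 0.85 |
| 36/60 | 0.94 | 0.05 | 0.85 |

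At 15/46, primary and factor are both significant in about 0.36 of trials, which is nearly every significant primary result. Primary and unaware-only are both significant in about 0.02. For guesser effects from 0.5 to 1.0 SD, the factor column at 15/46 runs from about 0.34 to 0.87.

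**The case against.** Four points on the other side carry weight.

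1. **The check is not reversed at high guessing rates.** A reader might infer that it always strengthens a demand-driven effect. It does so only for shares between 30% and 50%. At 36/60 it lowers the chance of significance from 0.94 to 0.85. That is the right direction, though far from the 0.05 in unaware participants.
2. **The 70% is not a rate of falsely reassuring reports.** The reporting rule in 7.4.2 also flags results that become significant. At 15/46 that happens in about 0.70 − 0.36 = 0.34 of trials.
3. **The same ANOVA gives a portion by aim-guessing term.** In the assumed case it is significant in about 70% of trials at 15/46. Primary and factor tests both significant with this term silent occurs in about 11%. This stands as a partial safeguard. However, the plan does not say it will be read, and its power for a difference of 0.45 SD, the size of the planned effect, is only about 28% at 14/46 and 36% at 19/60.
4. **Avoiding removal has a reason.** With 14 of 46 removed, power for the planned effect falls from 85% to about 70%; with the factor and equal effects in both groups it is about 79%. At N = 60 with 19 guessers the figures are about 80% and 89%.

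The scenario is also severe: 0.8 SD is about 1.8 times the planned effect (0.8/0.45), and no effect at all in unaware participants runs against the background evidence cited in section 1. It shows what the check could miss, not what is likely.

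**Conclusion.** The point holds in a limited form. Above 30% guessers, the marginal portion test planned in 7.4.2 does not estimate the effect in unaware participants at any guessing rate, and no other planned result does so. Under Type III weighting, guessers carry one half of the portion main effect, up to 1.64 times their primary-analysis weight at N = 46 (14 guessers). If they alone drove the effect, a significant primary result would almost always survive the check.

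The documents do not support the wider readings that the check runs backwards whenever guessing is common, or that one half also applies to portion size*SEP. The second depends on a model term that the plan leaves open. The rejection rates rest on an assumed guesser share, guesser effect and sum-of-squares type, and they concern the portion main effect only.

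The primary test is untouched and the rule applies only if the cover story fails for more than 30%. This is an inexpensive improvement to one conditional sensitivity analysis.

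**What to change.** In 7.4.2:
- At any guessing rate, report the portion effect and portion size*SEP in unaware participants, with 95% CIs.
- Above 30%, keep all participants in the model, crossed with SEP, and take these as simple effects at aim guessing = unaware, using the pooled error term. State the sum-of-squares type.
- Report the portion size*aim guessing interaction with its CI. Given its low power, do not read a non-significant result as evidence of no difference.
- Do not use the marginal portion or portion size*SEP tests from that model alone as the robustness result.

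The cost is a few sentences and extra contrasts from a model already planned, with no new data. The unaware-only interval is wider: at 15 of 46 guessers, about √(46/31) = 1.22 times the full-sample width for the same SD. Pooling the error adds degrees of freedom but does not recover that precision. Losing significance in unaware participants may therefore reflect lower power, so the estimate and interval should be read, not only the change in significance.
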